4.4 Exclusion criteria

Enrolled cases but meeting one of the following should be excluded:

- 1) Intraoperative exploration of the tumor has undergone dissemination or is unresectable;
- 2) Serious intraoperative or postoperative complications of surgical technique within 24h: bleeding or gastrointestinal leakage leading to shock;
- 3) Serious cardiac, pulmonary, cerebral or renal vital organ accidents or insufficiency during the operation or within 24h after the operation;
- 4) Postoperative pathology suggesting non-primary or metastatic hepatocellular carcinoma;
- 5) Patients in the control group who had more than 7 additional meals before bedtime;
- 6) Patients in the test group who did not have more than 7 bedtime refills during the follow-up period;
- 7) Those who voluntarily withdrew.

5. Research Methodology and Technical Approach

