(2) Postoperative: start drinking small amount of water on the 1st postoperative day, over to liquid diet after ventilation, and may over to autonomous semi-liquid diet + oral whole protein enteral nutrition during the day + LES program on the 2nd postoperative day. As the patient's voluntary intake meets 60% of the body's needs, the daytime oral enteral nutrition support can be gradually stopped and the LES program can be continued.

3) Discharge: daily intake needs to be on time according to the LES regimen.

Control group: no more food 1h before bedtime.

(1) Preoperative: same as the test group.

(2) Postoperative: start drinking small amount of water on the 1st postoperative day, over to liquid diet after ventilation, and can over to autonomous semi-liquid diet + oral whole protein type enteral nutrition during the day on the 2nd postoperative day. As the patient's voluntary intake meets 60% of the body's needs, enteral nutrition support can be gradually stopped.

(3) Discharge: Doctors judge whether the patients need to continue nutritional support according to their dietary recovery, and if they do, their nutritional supplementation should be completed before 1h

before bedtime.

2. biological sample collection:

Serum samples remaining after testing were collected from patients for metabolomics analysis.

3.Clinical information collection:

(1) General information collection: gender, age, height, weight, BMI, ICG15min retention time, name of surgery, duration of surgery, blood loss, blood transfusion, tumor stage, NRS2002, PG-SGA, GLIM malnutrition assessment (diagnosis) criteria diagnosis;

(2) Nutritional indicators collection: collect nutritional indicators such as serum albumin (ALB), prealbumin (PA), transferrin (TRF), and total serum protein (TP) on the 1st day of the subject's admission to the hospital, on the 6th day of the postoperative period, at 1 month after the operation, at 3 months after the operation, and at 6 months after the operation.

(3) Collection of liver function indexes: Liver function indexes such as alanine aminotransferase (ALT), alanine grass aminotransferase (AST), γ -glutamyltransferase (GGT), cholinesterase (CHE), and total bilirubin (TBIL) were collected on the first day of hospitalization, the sixth postoperative day, the first postoperative month, the third postoperative month and the sixth postoperative month of the subjects.

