6.1 Intake

Daily intake and time of intake were recorded during the perioperative period, and patients were followed up at 1 month postoperatively, 3 months postoperatively, and 6 months postoperatively for intake and time of intake.

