Adverse events (AEs), all adverse medical events that occur after a subject receives a late-night snack, which can be manifested as symptoms signs, illnesses, or abnormal laboratory tests, but are not necessarily causally related to the late-night snacks.

Serious Adverse Event (SAE), an adverse medical event such as death, life-threatening, permanent or severe disability or loss of function, subject requiring hospitalization or prolonged hospitalization, and

congenital anomalies or birth defects that occur after a subject receives late-evening snacks.

The investigator will closely observe or follow up the various reactions of the patients after performing the LES in order to detect adverse events or serious adverse events in a timely manner, and all adverse events such as bloating, diarrhea, etc., reported by the subjects or observed by the investigator during the period from enrollment to the end of the study or early withdrawal from the study must be documented in the medical record or CRF, including laboratory and ancillary investigations, and should include, at a minimum, the name of the AE, its occurrence time (to the nearest minute), end time (to the nearest minute), degree and frequency of episodes, whether or not treatment was corrected, the course of treatment and regression if treatment was documented, and the causal relationship to the study. All medical documentation related to the adverse event must be recorded in the original documentation, including copies of requests for laboratory tests and reports of test results. The name of the investigator must be signed and dated (to the nearest minute) on the original documents and written reports.

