A data safety monitoring program will be established for clinical studies according to the level of risk. All adverse events will be recorded in detail, appropriately handled and followed up until properly resolved or stabilized, and serious adverse events and unintended events, etc., will be reported to the Ethics Committee, the competent authority, the sponsor, and the drug regulatory authority in a timely manner according to the regulations; the principal investigator will conduct a cumulative review of all adverse events on a regular basis, and convene a meeting of the investigators to assess the risks and benefits of the study, if necessary; the injuries or discomfort is no more likely and no greater in magnitude than that encountered in daily life or than that of a routine examination, and that data and safety monitoring can be accomplished by the principal investigator.

10. Statistical processing

应用 SPSS26.0 统计软件对临床数据进行描述性统计，符合正态分布的计量资料以均数±标

准差($\bar{x} \pm s$)表示, 组间采用 t 检验, 不符合正态分布的计量资料以中位数(四分位间距) [M(IQR)] 表示, 组间采用 Mann-Whitney U 检验。计数资料用百分比[n(%)]表示, 组间比较采用卡方检验, $P<0.05$ 为有显著性统计学意义。采用 STATA12.0 中的 Kaplan-Meier 法计算各组复发率及无复发生存期, log-rank 检验进行组间比较。SPSS26.0 statistical software was applied to carry out descriptive statistics of the clinical data, and the measurements that conformed to normal distribution were expressed as mean \pm standard deviation ($\bar{x} \pm s$), and t-test was used between the groups, and the measurements that did not conform to normal distribution were expressed as median (inter-quartile spacing) [M(IQR)], and Mann-Whitney U-test was used between the groups. Count data were expressed as percentages [n(%)], and the chi-square test was used for between-group comparisons, with $P<0.05$ considered statistically significant. The Kaplan-Meier method in STATA 12.0 was used to calculate the recurrence rate and recurrence-free survival in each group, and the log-rank test was used for between-group comparisons.

11. Ethical principles of clinical research

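### Section 4.4 items 5–7 exclude enrolled patients for bedtime eating after group entry or for withdrawal, item 6 has two readings, and no planned analysis keeps these patients

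*Combined protocol and SAP*

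**What the plan says.** Section 4.4 is a second exclusion list, for patients already in the study: "Enrolled cases but meeting one of the following should be excluded". Items 1–4 concern findings at surgery, serious events during or within 24 h of it, and pathology. Items 5–7 are of another kind:

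- Item 5: "Patients in the control group who had more than 7 additional meals before bedtime". No period is given.
- Item 6: "Patients in the test group who did not have more than 7 bedtime refills during the follow-up period".
- Item 7: "Those who voluntarily withdrew".

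The statistical text (synopsis, section 3.2 under data analysis, section 5.1 item 5, section 10) names descriptive summaries, t, Mann-Whitney, chi-square and log-rank tests, and Kaplan-Meier estimates. It defines no full, per-protocol or safety set, no missing-data method and no sensitivity analysis.

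Section 6.1 records intake and its timing daily in the perioperative period. After that, "patients were followed up at 1 month postoperatively, 3 months postoperatively, and 6 months postoperatively for intake and time of intake".

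Section 3.1 describes open groups formed by patient preference. It plans 44 evaluable patients per group, raised to 53 for 20% dropout, and does not link that allowance to section 4.4.

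**The concern.** Bedtime eating and withdrawal happen after group entry and may be related to recovery. A test patient who stops the snack because of bloating or diarrhoea, for example, could drop out of the comparison of gastrointestinal symptoms, which the synopsis lists as a safety indicator. If items 5–7 govern the analysis, the albumin, complication, gastrointestinal and recurrence comparisons are all made in groups filtered on post-entry behaviour. Self-chosen groups are already confounded at baseline; this adds a second selection.

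Item 6 is also open to two meanings that set very different bars for staying in the test group. Neither item 5 nor item 6 can be counted night by night after discharge from the records that section 6.1 describes.

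**Working it through.** **The plan's own sample size.** From section 3.1: means 34.2 and 37.5 g/L (difference 3.3), SDs 3.9 and 5.4, two-sided 5%, power 90%. The root-mean-square SD is √((3.9² + 5.4²)/2) = 4.71 g/L. With the noncentral t, 44 per group gives power 0.90, so the stated 88 is reproduced. 44 × 1.2 = 52.8, hence 53. Losing 20% of 53 leaves 42.4, so 42.

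**What each reading of item 6 requires.** The follow-up period is not defined; I assume about 180 nights.

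- Excluded if 7 or fewer snacks were taken: at least 8 are needed, 8/180 = 4.4% of nights.
- Excluded if more than 7 were missed: at least 180 − 7 = 173 are needed, 173/180 = 96.1%.

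**How many of 53 test patients stay.** With independent nights and the same nightly adherence *a* for every patient (both assumed), snack nights X follow Binomial(180, *a*). The first reading excludes if X ≤ 7, the second if 180 − X ≥ 8. The last column instead lets adherence vary between patients (beta-binomial, concentration 5–10, assumed).

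| Mean adherence | First reading, kept | Second reading, uniform adherence | Second reading, varying adherence |
|---|---|---|---|
| 95% | essentially 53 | excluded 0.682; 53 × 0.318 = 16.8, about 17 kept | about 33–37 kept |
| 98% | essentially 53 | excluded 0.029, about 3% lost | about 12–15% lost |

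Uniform adherence overstates the loss at 95% and understates it at 98%, so the ranges should be read together.

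**Illustration of selection bias.** Assume no true effect, only the least adherent share *p* of the test group removed, and correlation *r* between adherence and albumin. The shift in the test mean is *r* × 4.71 × φ(z_p)/(1 − *p*). The false-positive rate is that of the two-sided 5% t-test against 53 controls.

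| Share removed (test n left) | φ(z_p)/(1 − p) | Shift, r = 0.2 to 0.5 | False-positive rate |
|---|---|---|---|
| 5% (50) | 0.109 | 0.10–0.26 g/L | 5.1–5.9% |
| 10% (48) | 0.195 | 0.18–0.46 g/L | 5.4–7.7% |
| 20% (42) | 0.350 | 0.33–0.82 g/L | 6.3–13.4% |

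The removal shares and correlations are assumed. Control removals under item 5 and withdrawals under item 7 could add to or offset these figures.

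**Dilution if everyone is kept.** If a share *q* of test patients does not adhere and gains nothing (assumed), the difference is 3.3 × (1 − *q*). Power is by noncentral t with SD 4.71.

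| q | Difference | Power, 53 per group | Power, 42 per group |
|---|---|---|---|
| 0 | 3.30 g/L | 0.95 | 0.89 |
| 10% | 2.97 g/L | 0.90 | 0.81 |
| 20% | 2.64 g/L | 0.82 | 0.72 |

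**The case against.** **The item 6 ambiguity may be a translation artefact, and context partly resolves it.** This stands in part. Item 5 allows controls up to 7 departures, so more than 7 missed is the symmetric counterpart, and section 3.2 requires the snack daily after discharge. Both favour the second reading. The literal English favours the first, and nothing in the readable text settles it.

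**Exclusion may not mean exclusion from analysis.** This stands. Section 4.4 sits under case selection and does not say. Even so, no readable section plans an analysis that retains these patients or their earlier data. Section 5.2 is a bare heading and some figures are not shown, so the statement is limited to the readable text.

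**An adherence-restricted comparison is a legitimate aim.** It can be, if stated and defined. Here it would arise only by default from an exclusion list. Keeping everyone does not restore comparability between self-chosen groups; it only avoids adding a further selection.

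**The 20% dropout allowance covers it.** It is not tied to section 4.4, and an allowance for numbers does not deal with selection.

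A reader might also infer that adverse events in excluded patients would be lost. The documents do not support that. Section 8 requires that events "during the period from enrollment to the end of the study or early withdrawal from the study must be documented in the medical record", and section 9 adds that "the principal investigator will conduct a cumulative review of all adverse events on a regular basis". What is missing is only a stated denominator for comparing the groups.

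**Conclusion.** This should be fixed. Items 5–7 exclude on post-entry behaviour and withdrawal, the meaning of exclusion is left open, and no readable section plans an analysis that keeps these patients. The two readings of item 6 can give very different test groups: at mean 95% adherence, essentially 53 against about 17 (uniform) or about 33–37 (varying). These counts rest on 180 nights, independence between nights and the assumed adherence.

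Two stronger conclusions are tempting and not supported. One is that the plan biases albumin in favour of the snack. Neither direction nor size can be derived from the documents. The 0.10–0.82 g/L and 5.1–13.4% above are an illustration, near nominal at the low end, and on the literal reading item 6 alone would remove few patients. The other is that the primary population is so undetermined that the comparison cannot stand. That would rest mainly on wording that may come from translation and that item 5 and the daily regimen partly clarify.

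**What to change.** 1. Remove items 5–7 as grounds for exclusion from analysis and leave items 1–4 as they stand. Items 1–3 arise at surgery or within 24 h after it, before the stage at which section 3.2 lists the snack for the test group ("and may over to autonomous semi-liquid diet + oral whole protein enteral nutrition during the day + LES program on the 2nd postoperative day"). Item 4 is a pathology result.
2. Make the primary analysis all enrolled patients not excluded under items 1–4, in the group chosen at enrolment, using all data up to withdrawal. State a method for missing albumin, for example multiple imputation from group, admission albumin and earlier-visit albumin, and show the complete-case result beside it.
3. Report gastrointestinal symptoms and complications in the same set, with its group sizes as denominators.
4. Reconcile the wording and period of items 5 and 6. Use one adherence definition for both groups, based on the section 6.1 records, only for a per-protocol sensitivity analysis. Which threshold was intended is for the investigators to settle.

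The cost is a revised list, a stated missing-data method, one sensitivity analysis and the dilution shown in the working. With 10% or 20% non-adherence, power is about 0.90 or 0.82 at 53 per group and about 0.81 or 0.72 at 42. State this power rather than enrol more. No new data are needed if adherence uses the section 6.1 records; a nightly count after discharge would need a diary.

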5.1 Research Methodology

1) Nutritional Assessment

All patients were screened for nutritional risk using the NRS 2002 scale within 24 h of admission, and a score of ≥ 3 was considered to be at nutritional risk; patients at nutritional risk were assessed for nutrition using the PG-SGA scale and diagnosed with malnutrition according to the GLIM Malnutrition Assessment (Diagnosis) Criteria.

2) Nutritional support therapy

The target intake for all patients was 25-30 kcal/kg/d. Nutritional supportive therapy was given to patients who were at nutritional risk and could not achieve the target intake. Oral nutritional supplements were preferred, and enteral nutritional supplementation was used in patients who still could not achieve 60% of the target amount. Supplemental parenteral nutrition was considered if patients could not achieve 60% of the target amount for 7 days after admission to the hospital.

3) Interventions

From the total daily intake, patients in the test group were divided into approximately 250kcal for late-evening snacks 1h before bedtime (200-275kcal total, 11.5g-18g protein, 25-55g complex carbohydrates); patients in the control group did not eat any more food 1h before bedtime.

Preparations used:

- ① Enteral nutrition powder: 450kcal/15.9g/100g;
- ② Whole protein type enteral nutrition suspension, energy density 1kcal/ml, protein 0.05g/ml, complex carbohydrate 0.126g/ml;
- ③ Whey protein powder, protein content >80g/100g.

[figure not shown]
4) Biological sample collection

Post-test residual serum samples from patients on day 1 of admission, day 6 postoperatively, 1 month postoperatively, 3 months postoperatively, and 6 months postoperatively were collected for metabolomic analysis to see if the metabolic pattern of the patients was altered in LES mode.

5) Clinical outcomes

The postoperative complication rate, tumor recurrence rate, recurrence-free survival, postoperative hospitalization time, total hospitalization cost, and cost of anti-infective drugs of the subjects after admission to the hospital were counted, and the chi-square test and independent samples t-test were performed to compare the differences, in order to find out whether the clinical outcomes had been improved under the LES model.

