2.1 Primary purpose

To observe the effects of late-evening snacks on the nutritional status, liver function recovery, complication rate and long-term prognosis of hepatocellular carcinoma patients who underwent hepatectomy, and to further explore the effects of late-evening snacks on the metabolic pattern of the patients through metabolomics, and to identify the serum differential metabolites, in order to initially investigate the potential mechanism of late-evening snacks to improve the nutritional status of the patients, and to provide theoretical basis for the development of an effective nutritional regimen in the clinic.

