2.3 Test hypothesis

It was hypothesized that there would be significant differences in serum albumin, prealbumin, and serum metabolic patterns in subjects in the test group compared to control patients, and potential mechanisms by which the LES would improve the nutritional status of patients would be identified.

3. Types of Research Designs and Experimental Steps

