3.1 Types of Research Designs

Types of study designs: single-center, prospective cohort studies

Research Center: Drum Tower Hospital, Medical School of Nanjing University

Grouping method: non-randomized, open, enrolled according to patients' wishes

[figure not shown]
Sample size calculation basis and formula:

This study was a single-center prospective cohort study with two groups, the test group and the control group, and the serum albumin level of the study subjects was the primary endpoint outcome indicator observed. Based on the review of previous literature^[28] and reference to the results of the pretest, it was expected that the albumin level before LES intervention was 34.2 ± 3.9 g/L and the albumin level

after LES intervention was 37.5 ± 5.4 g/L, with a two-sided $\alpha=0.05$ and a degree of certainty of $1-\beta=90\%$. Using PASS15 software can be calculated to obtain $n=88$ cases. Based on the 1:1 grouping, 44 subjects were needed in each of the test and control groups, and assuming a 20% subject dropout rate, the final minimum number of subjects needed was 53 in each of the test and control groups, for a total of at least 106 subjects included.

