7.1 Nutritional indicators

Primary Efficacy Indicator:

Serum albumin (ALB), recording ALB data from patient biochemical tests.

Secondary efficacy indicators:

Prealbumin (PA), alanine aminotransferase (ALT), glutamate aminotransferase (AST), serum gamma-glutamyl transpeptidase (GGT), cholinesterase (CHE), total bilirubin (TBIL), and C-reactive protein (CRP) were recorded, and the corresponding data in the patient's biochemical tests were recorded;

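### Only albumin is primary and powered, but the plan sets other outcomes beside it at P<0.05 with no testing order or limit on claims: across 13 non-primary outcomes the chance of a false result favouring the snack is about 17%

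*Combined protocol and SAP*

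**What the plan says.** - **Primary outcome.** The synopsis, section 3.1 and section 7.1 all name serum albumin as the single main indicator. The sample size in 3.1 is for albumin only.
- **Test hypothesis (2.3).** It expects that "there would be significant differences in serum albumin, prealbumin, and serum metabolic patterns in subjects in the test group compared to control patients". Section 7.1 lists prealbumin as secondary.
- **Primary purpose (2.1).** This covers "nutritional status, liver function recovery, complication rate and long-term prognosis of hepatocellular carcinoma patients who underwent hepatectomy". The metabolomics part of the same section is worded as exploration and initial investigation.
- **Clinical outcomes (5.1, item 5).** Complications, recurrence rate, recurrence-free survival, postoperative stay, total cost and anti-infective cost are compared "in order to find out whether the clinical outcomes had been improved under the LES model".
- **Statistical processing (10; same text in the synopsis and 3.2).** t, Mann-Whitney, chi-square and log-rank tests are named, and the only criterion is "with $P<0.05$ considered statistically significant". There is no testing order, alpha split, longitudinal model or statement on how secondary P values will be read.
- **Lists that differ.** Section 7.1 adds "serum gamma-glutamyl transpeptidase (GGT), cholinesterase (CHE), total bilirubin (TBIL), and C-reactive protein (CRP) were recorded" to the secondary indicators, whereas the synopsis list contains neither GGT nor CRP. Complications and length of stay are safety indicators in the synopsis but are tested for improvement in 5.1(5).

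**The concern.** The primary and secondary labels would normally limit what may be claimed. Here sections 2.1, 2.3 and 5.1(5) weaken that limit: one names a secondary and an exploratory outcome in the test hypothesis, another places liver function, complications and prognosis under the primary purpose, and the third frames six further tests as a check for improvement.

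Suppose albumin shows no difference. A single nominal P<0.05 on, say, total cost or complications could then be reported under 5.1(5) as an outcome improved by the snack, and nothing in section 10 would restrain that. The error rate behind such a statement is not the nominal one. Separately, if 2.3 is meant to require albumin and prealbumin together, the sample size was not calculated for that requirement.

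The point does not depend on which albumin visit is chosen. It would remain if one visit were fixed.

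**Working it through.** **1. Reproduce the plan's figure.** Inputs from 3.1: means 34.2 and 37.5 g/L (difference 3.3), SDs 3.9 and 5.4, two-sided 0.05, power 90%. Taken as a two-group comparison, the common SD is √((3.9² + 5.4²)/2) = √22.185 = 4.71. The noncentral t distribution gives power 0.895 with 43 per group and 0.901 with 44. So 44 per group, 88 in total, is reproduced, for albumin alone.

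**2. Count the non-primary outcomes.**
- Laboratory indicators with a visit schedule (6.2, 6.3, 7.1): prealbumin, ALT, AST, GGT, CHE, TBIL = 6
- Quality of life (6.5, 7.2) = 1
- Outcomes named in 5.1(5) = 6

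Total 6 + 1 + 6 = 13. CRP is left out because section 6 gives it no visit. Transferrin, total protein, albumin cost, gastrointestinal symptoms and the metabolites are also left out, so 13 is a low count.

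If each scheduled post-baseline visit were tested separately, the count would be 6×4 + 1×3 + 6 = 33. The plan does not say this. It is an assumption suggested by two-sample tests with no chosen visit and no longitudinal model.

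**3. False-positive rates.** Assume no true effect on any of these outcomes, comparable groups, and k test statistics with common correlation ρ, signed so that positive favours the snack. With c = 1.96:

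- Either direction: 1 − ∫ [Φ((c − √ρ·u)/√(1−ρ)) − Φ((−c − √ρ·u)/√(1−ρ))]^k φ(u) du
- Favouring the snack: the same without the second Φ term
- At ρ = 0 these reduce to 1 − 0.95^k and 1 − 0.975^k; for k = 13, 1 − 0.95¹³ = 0.487 and 1 − 0.975¹³ = 0.280

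| Tests | Event | ρ = 0 | ρ = 0.5 | ρ = 0.8 |
|---|---|---|---|---|
| 13 | either direction | 0.487 | 0.334 | 0.192 |
| 13 | favours snack | 0.280 | 0.167 | 0.096 |
| 33 | either direction | 0.816 | 0.528 | 0.264 |
| 33 | favours snack | 0.566 | 0.266 | 0.132 |

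The documents give no correlations, so ρ is assumed and shown as a range. A simulation with correlation only within blocks (laboratory tests, quality of life, clinical and cost outcomes; 0.3 to 0.8 between visits, 0.3 to 0.6 between outcomes) gives 20-25% for 13 tests and 30-48% for 33, favouring the snack. Both lie inside the ranges above.

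**4. Section 2.3 read two ways.**
- Either albumin or prealbumin suffices, one test each: the false-positive rate in either direction is 0.091 at ρ = 0.5 (0.078 at 0.8, 0.098 at 0), about 0.091/0.05 = 1.8 times alpha.
- Both are required: alpha is not inflated, but power falls. If prealbumin also has 90% power (assumed), the bivariate normal gives joint power 0.832 at ρ = 0.5 (0.810 at 0, 0.856 at 0.8). Adding a metabolic-pattern criterion could only lower it, and no test is defined for that.

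**The case against.** The plan has one primary outcome, powers it alone, and heads most of the others as secondary. Unadjusted secondary results beneath one primary are commonly reported as supportive. The study is an observational cohort whose purpose is to observe, and asking whether outcomes improved is a question rather than a claim. Much of this stands, and it rules out several stronger readings.

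- A reader might infer that there is no hierarchy or exploratory wording at all. There is: primary and secondary labels exist, and 2.1 describes the metabolomics as exploration. What is missing is an order or limit on claims beyond albumin, and 2.3 cuts across both labels.
- A reader might take 33% to 53% as the chance of a false improvement. Those figures count false results in either direction. Counting only results that favour the snack, the same model gives 17% and 27%.
- A reader might treat 33 tests as planned. The visits are a data schedule, and separate testing at each is not stated.
- A reader might infer that one significant liver enzyme would meet 2.3 or 5.1(5). Neither names a liver enzyme. Nor does prealbumin alone clearly meet 2.3, which joins its items with 'and'.

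The fixed sequence proposed below is one acceptable option among several. What the objection does not answer is that nothing in section 10 tells the analyst or reader how to treat a secondary P<0.05 when albumin is null. Allocation by patient choice calls for more restraint there, not less.

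**Conclusion.** The point holds as a gap in how results beyond albumin may be claimed, of moderate weight. With one test per outcome, the chance of at least one false result favouring the snack is 17% (10-28%), against 2.5% for a single two-sided test. In either direction it is 33% (19-49%). If each visit is tested separately, which is an assumption, the figures are 27% (13-57%) and 53% (26-82%). Under a joint reading of 2.3 the stated 90% power does not apply, and about 83% (81-86%) is the corresponding figure.

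All of these rest on assumed correlations and on comparable groups. Groups formed by patient choice and compared without adjustment may differ for other reasons, so the real rates could depart from these. That is a separate issue which the change below does not solve.

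**What to change.** 1. Rewrite 2.3 so that the between-group difference in albumin is the only primary hypothesis.
2. State in section 10 that prealbumin is tested only if albumin is significant: a fixed sequence, each at two-sided 0.05. This presumes one designated analysis for each outcome.
3. Label all other outcomes in 5.1(5), 7.1 and 7.2, and the metabolic pattern, as exploratory. Report each as a between-group difference with a 95% confidence interval, and make no claim of improvement on the strength of P<0.05. Reword 5.1(5) to match.
4. Use one identical secondary list in the synopsis and section 7. Settle whether GGT and CRP belong to it, and whether complications and length of stay are safety or efficacy outcomes.

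The cost is wording only, with no added patients or data. The downside is that a nominally significant secondary result can no longer be presented as proof of benefit.
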